##### **10.1.3.2 Consumables**

Materials tested to be compatible the study medication are listed in Table [10.1.3.2: 1](#) for preparation and in Table [10.1.3.2: 2](#) for administration.

Proprietary confidential information © 2021 Boehringer Ingelheim International GmbH or one or more of its affiliated companies

Table 10.1.3.2: 1      Overview of materials used for preparation of BI 765080 Powder for solution for injection/infusion 50 mg/vial (50 mg/mL)

Type	Qualitative composition
Syringe 50 mL intended for use with syringe pumps (Graduation: 1 mL)	Polypropylene
Syringe 10 mL (Graduation: 0.2 mL)	Polypropylene
Syringe 5 mL (Graduation: 0.2 mL)	Polypropylene
Syringe 3 mL; Graduation: 0.1 mL	Polypropylene; Plunger: PE
Syringe 1 mL (Graduation: 0.01 mL)	Polypropylene
Syringe closure	Polyethylene
20G 1½ needle	Stainless steel / Polypropylene
25G needle	Stainless steel / Polypropylene
Discofix-	PA

Table 10.1.3.2: 2      Reconstitution Medium and Dilution medium

Description	Purpose
Water for Injection	Reconstitution of lyophilized powder
0.9% Saline Solution	Diluting the reconstituted drug product prior administration

### 10.1.3.3 Preparation of the study medication

In order to achieve the target doses after reconstitution with water for injection the drug product must be further diluted using isotonic saline to the concentrations assigned for each dose level. The target doses will be achieved by volume aliquot. Further information on the concentrations to be administered per dose level and the resulting volume aliquot to be administered are provided in Table [10.1.3.3: 1](#).

**Please note:** In order to prepare dilutions with a concentration of 0.1 mg/mL 2 dilution steps are required.

Proprietary confidential information © 2021 Boehringer Ingelheim International GmbH or one or more of its affiliated companies

Table 10.1.3.3: 1 Dilution Scheme

Dose level	Target Dose [mg]	Target Concentration [mg/mL]	VBI 765080 [mL]	V0.9% Saline [mL]	Administration Volume [mL]
1	1	0.1	1	49	--
			5	45	10
2	10	1	1	49	10
3	25				25
4	50				50
5	100	2	2	48	50
6	200	4	4	46	50

The site may prepare syringes containing an overfill as per site standard policies. The overfill is required in order to accommodate the dead volume of the infusion set.

Administration of the ready to use syringes will be done according to Section [4](#).

Proprietary confidential information © 2021 Boehringer Ingelheim International GmbH or one or more of its affiliated companies

#### 10.1.3.3.1 Reconstitution of the lyophilized powder

1. Attach a 3 mL syringe to the bottle containing water for injection (WFI) and withdraw 1.2 mL WFI.
2. Attach a 20G needle to the syringe and adjust the volume to 1.1 mL and gently inject the complete content of the syringe through the stopper, to the wall of the vial containing BI 765080 powder for solution for injection / infusion (50mg/vial).
3. Discard needle and syringe, and then gently swirl the vial until the lyophilizate is dissolved and homogenized. Do not shake. Avoid the generation of foam. The full reconstitution should be finished within 10 minutes.
4. In case of foam generation during reconstitution, wait with further processing until foam has settled. This should take not more than 60 min.

#### 10.1.3.3.2 Dilution Procedure (DL 1)

1. Withdraw the volume aliquot of 0.9% saline defined in Table [10.1.3.2: 2](#) in a 50 mL syringe (compatible with syringe pump).
2. Withdraw the drug product volume defined in Table [10.1.3.2: 2](#) from the vial containing reconstituted BI 765080 50 mg / mL using an appropriate syringe.
3. Combine both syringes with a syringe adapter and mix the content of the syringes by gently transferring back and forth gently transferring back and forth 10 times. The resulting concentration is 1 mg/ mL.
4. Transfer 5 mL of the diluted drug product in a 5 mL syringe and discard the 50 mL syringe.
5. Withdraw 45 mL isotonic saline in a 50 mL syringe (compatible with syringe pump), combine both syringes via syringe adapter / discofix connector and mix the content of both syringes by gently transferring back and forth 10 times. The resulting concentration is 0.1 mg/ mL.
6. Collect the complete volume in the 50 mL syringe. Make sure that the complete volume has been transferred to the 50 mL syringe prior disconnecting the smaller syringe and the adapter. Lock the syringe using a syringe closure.

#### 10.1.3.3.3 Dilution Procedure (DL 2-6)

1. Withdraw the volume aliquot of 0.9% Saline defined in Table [10.1.3.2: 2](#) in a 50 mL syringe (compatible with syringe pump).
2. Pool the drug product volume defined in Table [10.1.3.2: 2](#) from the vials containing reconstituted BI 765080 50 mg/mL using an appropriate syringe.
3. Combine both syringes with a syringe adapter / discofix connector and mix the content of the syringes by gently transferring back and forth gently transferring back and forth 10 times
4. Collect the complete volume in the 50 mL syringe. Make sure that the complete volume has been transferred to the 50 mL syringe prior disconnecting the smaller syringe and the adapter. Lock the syringe using a syringe closure.

#### 10.1.3.3.4 Preparation of Placebo

Note: Commercially available 0.9% Saline for injection will be used as Placebo.

1. Withdraw the amount 0.9% Saline for Injection matching the administration volume of active drug product defined in Table [10.1.3.2: 2](#) in a 50 mL syringe (compatible with syringe pump).

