### **3.2 DISCUSSION OF TRIAL DESIGN, INCLUDING THE CHOICE OF CONTROL GROUP**

For single-rising dose trials, the rising dose design described in Section [3.1](#) is viewed favourably under the provision not to expose the subjects involved to undue risks.

Single-blind conditions regarding the subject's treatment (active or placebo) are maintained within each dose group. However, subjects and investigators will be aware of the dose of drug administered. The disadvantage of the trial design is a possible observer bias with regard to the dose-dependent effects; in addition, the sequential dosing of groups could potentially result in time-related effects. However, as such effects are expected to be small relative to the differences between the doses in the broad range investigated, unbiased comparisons between treatments can still be expected.

It is standard in single or multiple rising dose trials involving healthy volunteers to include a placebo group to control for safety, tolerability, [REDACTED] effects of the trial medication. Each dose group consists of 8 subjects, with 6 on active treatment, and 2 on placebo. For data analysis purposes, the placebo control group will include all subjects of all dose groups treated with placebo. Six subjects per active treatment group are generally considered to be sufficient for the exploratory evaluation of pharmacokinetics.

The administration of the study drug as i.v. infusion is considered advantageous since the administration of BI 765080 can be immediately stopped in case safety concerns arise during the running infusion. A further advantage of the i.v. route is the possibility to investigate supratherapeutic exposure unbiased from individual variability in bioavailability.

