#### 4.1.4 Drug assignment and administration of doses for each subject

The treatments to be evaluated are outlined in Table [3.1: 1](#) and Appendix [10.1](#), Table [10.1.3.3: 1](#). The dose volume for placebo corresponds to the dose volume of the corresponding dose level. Subjects receiving placebo are equally distributed across dose groups. Start- and end time of the infusion will be recorded.

Detailed instructions for the dilution of the trial product, the preparation of the infusion solution, the volume to be administered and the infusion time is provided in Appendix [10.1](#). In all subjects, the infusion solution will be intravenously administered over 30 minutes approximately between 8.00 h and 10.00 h of the respective study day.

In case of safety concerns, e.g. due to infusion reactions, it is in the discretion of the investigator or his/her designee to adapt the infusion scheme, including but not limited slowing down the infusion rate, stopping of the infusion and provided no further safety concern exist restarting at a slower rate. Further based on █ medical judgment he/she will provide medications such as steroids, etc. as needed.

For administration of the infusion, an intravenous indwelling catheter is placed into an arm vein of the subject and closed with a mandrin. A second indwelling catheter used for collection of blood samples will be placed on the contralateral arm.

The administration of the trial medication will be done under supervision of the investigating physician or a designee. For drug administration, the so-called four-eye principle (two-person rule) should be applied. For this, one authorised employee of the trial site should witness the administration of trial medication, and – if applicable – its preparation (e.g. reconstitution), if correct dosage cannot be ensured otherwise. For the purpose of drug accountability, the infusion set will be weighed before and after drug administration.

Water is allowed except for 1 hour before start of infusion and 1.5 h after end of infusion. On Day 1, from 2 hours post-dose, liquid intake is restricted at additional 3000 mL until the morning of Day 2. Standardised meals will be served as outlined in the [Flow Chart](#). Subjects will be kept under close medical surveillance until 48 h following drug administration. On

Proprietary confidential information © 2021 Boehringer Ingelheim International GmbH or one or more of its affiliated companies

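### At dose levels 1 to 3 the preparation steps leave active and placebo syringes with different fills (50 mL against 10, 10 and 25 mL), which could weaken the subject blind unless the syringes are masked

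*Protocol*

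**What the plan says.** Section 3.2 of the protocol says that single-blind conditions regarding the subject's "treatment (active or placebo) are maintained within each dose group". Section 4.1.5.1 adds that subjects know the dose level but not the treatment, and that investigators and the sponsor's trial functions know the treatment.

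On volume, Section 4.1.4 states: "The dose volume for placebo corresponds to the dose volume of the corresponding dose level". Section 10.1.3.3 says of the active product: "The target doses will be achieved by volume aliquot". Its Table 10.1.3.3: 1 gives administration volumes of 10, 10, 25, 50, 50 and 50 mL for dose levels 1 to 6.

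The procedures then diverge:

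- **Active, level 1 (10.1.3.3.2).** In the last dilution, 5 mL of the intermediate solution is mixed with 45 mL saline. The whole volume is collected in the 50 mL pump syringe, which is then locked.
- **Active, levels 2 to 6 (10.1.3.3.3).** The preparer is told: "Collect the complete volume in the 50 mL syringe", and then: "Make sure that the complete volume has been transferred to the 50 mL syringe prior disconnecting the smaller syringe and the adapter". The syringe is then locked.
- **Placebo (10.1.3.3.4).** "Withdraw the amount 0.9% Saline for Injection matching the administration volume of active drug product", again in a 50 mL pump syringe.
- **Infusion (10.1.4.1).** The whole content of the container is given over 30 minutes.

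All three preparation procedures send the reader to Table 10.1.3.2: 2 for volumes. That table lists the reconstitution and dilution media and holds no volumes.

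**The concern.** Active and placebo go into the same type of syringe on the same type of pump. If the active syringe holds 50 mL and the placebo syringe 10 or 25 mL, the fill level differs by treatment within a dose group. Subjects already know their dose level, so within a group a difference in fill can reflect only treatment.

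The subject's blind matters because part of the safety data comes from the subject. Under Section 5.2.6.2.1 adverse events come from spontaneous reports and non-specific questioning, and under Section 5.2.5.1 pain is one of the local tolerability items. A subject who believes he knows his treatment may report differently. Placebo subjects are pooled across dose groups (Protocol 7.3.4, SAP 6.1), so any distortion at levels 1 to 3 would enter the comparator for all six doses.

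**Working it through.** **Inputs.** Drug, saline and administration volumes are from Table 10.1.3.3: 1. The second dilution step at level 1 is also spelled out in 10.1.3.3.2. The reconstituted product is 50 mg/mL (10.1.3.3.2 and 10.1.3.3.3). Group and cohort sizes are from Section 3.1.

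**Step 1: reproduce the dilution scheme.** Concentration = mg of drug / (drug volume + saline volume); dose = concentration × administration volume.

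- Level 1: 1 mL × 50 mg/mL / 50 mL = 1 mg/mL; then 5 mL × 1 mg/mL / 50 mL = 0.1 mg/mL; 0.1 × 10 = 1 mg.
- Levels 2 to 4: 1 × 50 / 50 = 1 mg/mL; × 10, 25 and 50 mL = 10, 25 and 50 mg.
- Level 5: 2 × 50 / 50 = 2 mg/mL; × 50 = 100 mg.
- Level 6: 4 × 50 / 50 = 4 mg/mL; × 50 = 200 mg.

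All six target doses reproduce, so the table is consistent with itself.

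**Step 2: compare the prepared syringes, before any overfill.** Active fill = drug volume + saline volume in the last step. Placebo fill = administration volume.

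| Dose level | Active fill (mL) | Placebo fill (mL) | Difference (mL) | Ratio |
|---|---|---|---|---|
| 1 | 5 + 45 = 50 | 10 | 40 | 5:1 |
| 2 | 1 + 49 = 50 | 10 | 40 | 5:1 |
| 3 | 1 + 49 = 50 | 25 | 25 | 2:1 |
| 4 | 1 + 49 = 50 | 50 | 0 | 1:1 |
| 5 | 2 + 48 = 50 | 50 | 0 | 1:1 |
| 6 | 4 + 46 = 50 | 50 | 0 | 1:1 |

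**Step 3: look for a step that removes the difference.** None follows the final mixing. Level 1 shows that the text writes out an aliquot where it means one: 5 mL of the intermediate dilution is transferred and the rest discarded. Section 10.1.3.3 allows an overfill, but its purpose is the dead volume of the infusion set, its size is not given, and it is not limited to active syringes. Nothing suggests that it closes a gap of 25 to 40 mL.

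**Step 4: count the subjects.**

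- Levels 1 to 3: 3 × 8 = 24 of 48 subjects, made up of 3 × 6 = 18 active and 3 × 2 = 6 of the 12 placebo subjects.
- Cohort 1 has one active and one placebo subject, cohort 2 has two active, and cohort 3 has three active and one placebo. Same-day contrast is possible in cohorts 1 and 3 only: 3 × (2 + 4) = 18 subjects.

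**Step 5: set the infusion instruction beside the table.** If the complete 50 mL were given at levels 1 to 3, the amounts would be 0.1 × 50 = 5 mg, 1 × 50 = 50 mg and 1 × 50 = 50 mg, against targets of 1, 10 and 25 mg. Collecting the whole dilution and infusing the whole container therefore cannot both stand beside the table's administration volumes. The passages contradict each other; this review takes no position on which is right.

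**The case against.** The strongest reply is that the mismatch is a drafting artefact. Read together, the volume-aliquot sentence in 10.1.3.3 and the complete-content instruction in 10.1.4.1 suggest that the container is meant to hold the administration volume. On that reading active and placebo fills are equal, and the placebo sentence is already right. The difference in fill then comes from the active text, not from 10.1.3.3.4. This stands in part: the fill question cannot be settled apart from the conflict among 10.1.3.3, 10.1.3.3.2, 10.1.3.3.3 and 10.1.4.1. It does not remove the point, because a preparer who follows the active steps as written ends with 50 mL.

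A second reply is that a subject has nothing to compare with. He receives one infusion, knows the dose level, and is nowhere said to know the expected volume. The documents do not say whether the syringe is in view or whether one subject sees another's infusion; the 10-minute spacing in cohort 3 is only a minimum interval. This also stands. A reader might infer that subjects can tell placebo from active in half the trial. The text does not support that: silence about masking is not evidence that syringes are visible, and cohort 2 offers no same-day contrast.

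Third, drug-relatedness is judged by investigators who know the treatment by design, so loss of the subject blind reaches the primary endpoint only through what subjects report. The analysis is descriptive with no hypothesis tests. Both facts limit the consequence.

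**Conclusion.** The point holds as a gap in the preparation instructions. As written, active and placebo fills differ at dose levels 1 to 3 (50 mL against 10, 10 and 25 mL): 3 of 6 groups, 24 of 48 subjects and 6 of 12 pooled placebo subjects. The more plausible setting for recognition, with active and placebo dosed on the same day, covers 18 subjects.

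Whether the blind is weakened rests on two things that the documents do not state: that the site follows the steps literally, and that the syringe is visible and unmasked. If either fails, the subject blind is unaffected. If both hold, some subjects could recognise their treatment, with possible bias in self-reported adverse events and local tolerability. The documents give no basis for putting a number on that bias.

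The point remains worth acting on because the change is nearly free and protects a blind that Sections 3.2 and 4.1.5.1 rely on.

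**What to change.** 1. Reconcile 10.1.3.3 (with Table 10.1.3.3: 1), 10.1.3.3.2, 10.1.3.3.3 and 10.1.4.1 so that they agree on what the active container holds at dose levels 1 to 3 and what is infused from it. That decision belongs to the sponsor.
2. Then state in 10.1.3.3.4 that the placebo syringe has the same total fill, pumped volume and rate as the active syringe of that dose level under the reconciled text.
3. In 10.1.3.3.2, 10.1.3.3.3 and 10.1.3.3.4, replace the reference to Table 10.1.3.2: 2 with Table 10.1.3.3: 1.

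**Cost.** Text edits in Appendix 10.1 and at most 50 − 10 = 40 mL more saline per placebo syringe, or none if the reconciled active fill equals the administration volume. Step 2 must not be made alone: if placebo were filled to 50 mL while 10.1.4.1 still called for the complete content, placebo subjects at levels 1 to 3 would receive more than the volume that Section 4.1.4 ties to their dose level. The wording of 10.1.4.1 therefore has to be aligned in the same edit.

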#### 10.1.3.4 In-Use stability statement

Chemical and physical in-use stability of BI 765080 has been demonstrated for a concentration range from 0.1 mg/mL to 8 mg/mL diluted with 0.9% saline solution for 24 hours at 2-8°C (36-46°F) followed by 6 h (4 h storage and 2 h infusion time) at 30°C (86°F) in clinical sets as described. Do not freeze.

From a microbiological point of view, the solution for infusion should be used immediately. The solution for infusion is not intended to be stored unless dilution has taken place under controlled and validated aseptic conditions. If not used immediately, in-use storage times and conditions are the responsibility of the user.

### 10.1.4 Infusion Instructions

#### 10.1.4.1 General Remarks

In order to avoid an infusion reaction caused by the administration of low temperature solution the infusion container must be brought to room temperature before infusion.

Connect the infusion set (= infusion container connected with administration set and 0.2 µm in-line filter) with the catheter and administer the complete content of the infusion container over 30 min to the subject.

In case of technical issues or complications during infusion, please refer to the protocol.

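### Protocol Appendix 10.1: at dose levels 1–3 the active syringe holds 50 mL and the infusion instruction is to give all of it, so the literal dose is up to 5, 50 and 50 mg instead of 1, 10 and 25 mg

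*Protocol*

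**What the plan says.** All the text is in the Protocol.

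- **Dose table.** Table 10.1.3.3: 1 lists, by dose level, the target dose, concentration, volumes mixed and administration volume. The mixed volume is 50 mL. The administration volumes are 10, 10, 25, 50, 50 and 50 mL. The text above the table says that "the resulting volume aliquot to be administered are provided in Table" 10.1.3.3: 1.
- **Active preparation.** Section 10.1.3.3.2 (level 1) ends with "Collect the complete volume in the 50 mL syringe", after which the syringe is locked. Section 10.1.3.3.3 (levels 2–6) ends in the same way.
- **Placebo preparation.** Section 10.1.3.3.4 draws up saline "matching the administration volume of active drug product defined in Table" 10.1.3.2: 2, so the placebo syringe holds the administration volume only.
- **Infusion.** Section 10.1.4.1 says to "administer the complete content of the infusion container over 30 min to the subject".
- **Cross-references.** Section 10.1.3.3 says "Administration of the ready to use syringes will be done according to Section" 4. Section 4.1.4 says "the volume to be administered and the infusion time is provided in Appendix" 10.1. It also states: "The dose volume for placebo corresponds to the dose volume of the corresponding dose level".
- **Overfill.** Section 10.1.3.3 lets the site overfill syringes and explains: "The overfill is required in order to accommodate the dead volume of the infusion set". No amount is given.

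**The concern.** At levels 1–3 the dose is set by how much of the 50 mL is infused. No active-drug step expels the excess, transfers an aliquot or sets a pump volume, and the only instruction at the point of infusion is to give everything. The table and the procedure therefore give different doses.

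The consequences of following the procedure literally are:

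- The first active subject in this first-in-human trial could receive up to 5 mg against a planned start of 1 mg.
- Level 2 could receive up to 50 mg, which is the level 4 dose. Levels 2, 3 and 4 would then all be at about 50 mg, so those escalation steps would disappear. The dose-proportionality power model in Section 7.1 would be distorted if it used the nominal doses.
- Active subjects would receive 50 mL against 10, 10 or 25 mL for placebo. That contradicts the volume matching in Section 4.1.4 and could weaken the subject blind.

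**Working it through.** **Inputs.** The reconstituted stock is 50 mg/mL (Sections 10.1.3.3.2 and 10.1.3.3.3). Mixing and administration volumes come from Table 10.1.3.3: 1. In the available text the concentration and mixing cells for levels 3 and 4 are blank. I read them as merged with level 2 (1 mL drug plus 49 mL saline). The target doses support this: 25 mg / 25 mL = 1 mg/mL and 50 mg / 50 mL = 1 mg/mL.

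**Step 1: concentrations** (stock × drug volume / total volume).

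- Level 1, two dilutions: 50 × 1/50 = 1 mg/mL, then 1 × 5/50 = 0.1 mg/mL
- Levels 2–4: 50 × 1/50 = 1 mg/mL
- Level 5: 50 × 2/50 = 2 mg/mL
- Level 6: 50 × 4/50 = 4 mg/mL

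These match the table.

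**Step 2: intended dose** (concentration × administration volume) **and literal dose** (concentration × 50 mL).

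| Level | Conc. (mg/mL) | Admin. volume (mL) | Intended dose (mg) | Literal dose, upper bound (mg) | Ratio |
|---|---|---|---|---|---|
| 1 | 0.1 | 10 | 1 | 5 | 5 |
| 2 | 1 | 10 | 10 | 50 | 5 |
| 3 | 1 | 25 | 25 | 50 | 2 |
| 4 | 1 | 50 | 50 | 50 | 1 |
| 5 | 2 | 50 | 100 | 100 | 1 |
| 6 | 4 | 50 | 200 | 200 | 1 |

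The intended column reproduces all six target doses, so the table is internally correct.

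**Step 3: allowance for dead volume.** The documents give no figure. As an assumption, let an unprimed line hold back d = 0 to 5 mL. The literal dose is then concentration × (50 − d):

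- Level 1: 4.5–5 mg (4.5–5 times intended)
- Level 2: 45–50 mg (4.5–5 times)
- Level 3: 45–50 mg (1.8–2 times)

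Dead volume does not account for the discrepancy. The excess over the administration volume is 50 − 10 = 40, 50 − 10 = 40 and 50 − 25 = 25 mL.

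**Step 4: the opposite error.** If a correction simply pumped the administration volume V into an unprimed line, the under-dose would be d/V. With d = 2 mL this is 2/10 = 20% at levels 1 and 2 and 2/25 = 8% at level 3. Over d = 0 to 5 mL it is 0–50% and 0–20%. This does not describe the current text, but it affects how the fix should be worded.

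**Step 5: the table references.** The preparation steps cite Table 10.1.3.2: 2 five times for volumes (two in Section 10.1.3.3.2, two in 10.1.3.3.3, one in 10.1.3.3.4). That table lists the reconstitution and dilution media and holds no volumes.

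**The case against.** The best counter-argument is that this is an omitted step and the intention is not in doubt. Section 10.1.3.3 says doses are reached through the aliquot given. The opening sentence of Section 4.1.4 names Table 10.1.3.3: 1 directly, so a reader sent to Section 4 can reach 10, 10 and 25 mL. An overfill allowance makes sense only for a syringe filled nominally to the administration volume, and placebo is prepared on that basis. On this reading the infusion container is the finished aliquot, and giving all of it is correct. Preparation also follows site procedures that are not in these documents. Section 4.1.4 advises a two-person check. The literal doses stay within the planned range, and Section 1.3.2 reports no adverse effects in rats or monkeys up to 100 mg/kg.

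Much of this stands. The intended dose is clear, the wrong table references are clerical on their own, and the dead-volume figures are assumptions. It does not remove the conflict. No written step for active drug produces the aliquot syringe that this reading needs: the only container described is the locked 50 mL syringe. The overfill is tied to dead volume and does not plausibly explain 25 to 40 mL. Section 4.1.4 points to the table but neither supplies the missing step nor changes the infusion instruction. A two-person check against conflicting instructions is a weak safeguard. Weighing the infusion set, also in Section 4.1.4, would reveal the excess only after the dose was given.

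**Conclusion.** The concern holds. At levels 1, 2 and 3 the procedure as written gives at most 5, 50 and 50 mg against 1, 10 and 25 mg in the table. Levels 4–6 are not affected. The upper bounds assume that the syringe content is delivered in full and that the level 3 mixing cells are shared with level 2. The ranges in steps 3 and 4 depend also on the assumed 0–5 mL dead volume and an unprimed line.

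This is an inconsistency in the written instructions and is not evidence of a dosing error. The clear table limits the practical risk. It should still be corrected, because the bedside instruction in a first-in-human escalation gives the wrong dose when it is followed.

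**What to change.** 1. Add a final step to Sections 10.1.3.3.2 and 10.1.3.3.3: at levels 1–3, reduce the active syringe to the Table 10.1.3.3: 1 administration volume plus a stated dead-volume overfill. Fill the placebo syringe to the same volume. The excess of 40, 40 and 25 mL leaves ample solution for the overfill.
2. Reword Section 10.1.4.1 so that the administration volume in Table 10.1.3.3: 1 is what reaches the subject over 30 min. State whether the line is primed with study solution or flushed afterwards, so that the correction does not cause the under-dose in step 4.
3. Change the five references in Sections 10.1.3.3.2 to 10.1.3.3.4 from Table 10.1.3.2: 2 to Table 10.1.3.3: 1.

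The cost is a wording change in one appendix and a short site briefing. The sponsor must state the dead volume of the tubing and filter set. No extra subjects or trial procedures are needed.
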